Grade 3 or 4 (despite maximal anti-diarrheal medication)	Omit dose until resolved to $\leq$ grade 1, then resume treatment at $\downarrow$ 1 dose level
Vomiting Grade 1 (despite appropriate anti-emetics) Grade 2 (despite appropriate anti-emetics)	Maintain dose level Omit dose until resolved to $\leq$ grade 1, then maintain dose level. If vomiting returns as $\geq$ grade 2, then omit dose until resolved to $\leq$ grade 1, then $\downarrow$ 1 dose level.
Grade 3 (despite appropriate anti-emetics) Grade 4 (despite appropriate anti-emetics)	Omit dose until resolved to $\leq$ grade 2, then $\downarrow$ 1 dose level Omit dose until resolved to $\leq$ grade 2, then $\downarrow$ 1 dose level
Nausea Grade 1 or 2 (despite appropriate anti-emetics) Grade 3 (despite appropriate anti-emetics)	Maintain dose level Omit dose until resolved to $\leq$ grade 1, then $\downarrow$ 1 dose level

Recommended dose modifications for INC280	
Worst toxicity CTCAE Grade a	During a cycle of therapy
SKIN AND SUBCUTANEOUS TISSUE DISORDERS	
Rash/photosensitivity***	
Grade 1	Maintain dose level.
Grade 2	Maintain dose level.
Grade 3, despite skin toxicity therapy	Omit dose until resolved to grade $\leq$ 1, then: If resolved in $\leq$ 7 days, then $\downarrow$ resume treatment at 1 dose level If resolved in $>$ 7 days (despite appropriate skin toxicity therapy), then discontinue patient from study drug treatment
Grade 4, despite skin toxicity therapy	Mandatory: Omit dose and discontinue patient from study drug treatment
RESPIRATORY DISORDERS	
Interstitial Lung Disease (ILD) /Pneumonitis	
Monitor patients for pulmonary symptoms indicative of ILD/Pneumonitis. In addition, withhold INC280 for acute onset of new or progressive unexplained pulmonary symptoms, such as dyspnea, cough and fever and during diagnostic workup for ILD/Pneumonitis to exclude alternative causes such as, but not limited to infections, lymphangitic carcinomatosis, cardiogenic edema, or pulmonary hemorrhage.	
Grade 1	
Interrupt INC280 during diagnostic workup for ILD/Pneumonitis. Exclude infections and other etiologies.
 
In presence of diagnosis of ILD/Pneumonitis after diagnostic workup, it is mandatory to permanently discontinue INC280.
 
Only in absence of diagnosis of ILD/Pneumonitis, study drug may be restarted at the same dose.
 
If it recurs after restarting of study drug, permanently discontinue INC280.

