CARDIAC $\geq$ CTCAE grade 3  QTcF $\geq$ 501 ms (CTCAE grade 3)	Test weekly (or more frequently) until $\leq$ CTCAE grade 2.  When QTcF $\geq$ 501 ms (CTCAE grade 3), perform the following: 

Call the study's central ECG review laboratory immediately and request an immediate manual read of the ECG.

Perform an analysis of serum potassium, calcium, phosphorus, and magnesium, and if below lower limit of normal, correct with supplements to within normal limits.

Review concomitant medication usage for the potential to inhibit CYP3A4/5 (Table 6-5) and/or to prolong the QT-interval (Table 6-6).

Check compliance with correct dose and administration of INC280.

 Perform a repeat ECG within one hour of the first QTcF of $\geq$ 501 ms. 

If QTcF remains <math>\geq</math> 501 ms, repeat ECG as clinically indicated, but at least once daily until the QTcF returns to <math><</math> 501 ms.

 Repeat ECGs 7 days and 14 days (and then every 21 days) after dose resumption for all patients who had therapy interrupted due to QTcF $\geq$ 501 ms. 

If QTcF of <math>\geq</math> 501 ms recurs, repeat ECGs as described above.

 Notes: 

The investigator should contact the Novartis Medical Lead or designee regarding any questions that arise if a patient with QTcF prolongation should be maintained on study.

If the central ECG report shows a QTcF <math>\geq</math> 501 msec (not previously documented on the site machine), contact the patient and instruct him/her to suspend INC280 and return for a repeat ECG as soon as possible. The central ECG reader should be called for a manual read of the repeat ECG immediately, and the above guidance followed.

TOXICITY	FOLLOW-UP EVALUATION
GASTROINTESTINAL	

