Diarrhea	
Initiate anti-diarrhea treatment after first signs of abdominal cramping, loose stools or overt diarrhea.
 
Consider/Investigate potential concomitant medication, food or comorbidity driven causes of diarrhea (including infectious causes) and remedy these causes if possible (e.g. discontinuation of concomitant medication, dietary modification, treatment of comorbidity).
 
The patient should be monitored for signs of dehydration and instructed to take preventive measures against dehydration as soon as diarrhea occurs. Antidiarrheal medication must be initiated at the first sign of abdominal cramping, loose stools or overt diarrhea. Concomitant medication for the treatment of diarrhea should follow local practice and the investigator's best judgment and may follow "the recommended guidelines for the treatment of cancer treatment-induced diarrhea" (Benson et al 2004). For example:
 
 
For uncomplicated diarrhea (grade 1 or 2 without complicating signs or symptoms), loperamide given at a standard dose (e.g. initial administration of 4 mg, then 2 mg every 2-4 hours, maximum of 16 mg/day), along with oral hydration and dietetic measures should be considered. Note: complicating signs or symptoms include: moderate to severe cramping, decreased performance status, fever, neutropenia, frank bleeding or dehydration.
 
For complicated diarrhea (all grade 3 or 4, grade 1-2 with complicating signs or symptoms), management should involve intravenous (IV) fluids, and consider treatment with octreotide (at starting dose of 100 to 150 µg sub-cutaneous tid or 25 to 50 µg IV) and antibiotics (e.g. fluoroquinolone) should be given.
 

Nausea and Vomiting	
The investigator should consider/investigate potential concomitant medication, food or comorbidity driven causes of nausea and/or vomiting and remedy these causes if possible (e.g. discontinuation of concomitant medication, dietary modification, treatment of comorbidity).
 
Individualized supportive and anti-emetic treatment should be initiated, as appropriate, at the first signs and/or symptoms of these AEs. In patients with vomiting, the patient should be monitored for signs of dehydration and instructed to take preventive measures against dehydration.
 
Concomitant medication for the treatment of nausea and/or vomiting should follow local practice and the investigator's best judgment.

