## 6.4 Concomitant medications

Drugs in [Table 6-5](#) and [Table 6-6](#) are presented by mechanism of interaction. [Table 6-7](#) presents drugs known to cause Torsades des Pointes.

In general, the use of any concomitant medication/therapy deemed necessary for the care of the patient (e.g. such as anti-emetics, anti-diarrhea) is permitted (see [Section 6.4.1](#)), except when specifically prohibited (see [Section 6.4.3](#)).

The patient must be told to notify the investigational site about any new medications he/she takes after the start of the study drug. All medications (excluding study treatment and prior antineoplastic treatments), blood transfusions, surgeries and procedures (including physical therapy) administered within 28 days prior to the first dose administration of INC280 through 30 days after the last dose of INC280 will be recorded in the Concomitant Medications or Surgical and Medical Procedures eCRF, respectively. Medications include not only physician prescribed medications, but also all over-the counter medications, herbal medications, food supplements and vitamins.

The following restrictions apply during the entire duration of the study:

- No other investigational therapy should be given to patients
- No anticancer agents other than the study medication (INC280) should be given to patients.

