**Table 6-6 Drugs prohibited while on study**

Mechanism of Interaction	Drug Name
Strong CYP3A4 inducer	carbamazepine, enzalutamide, lumacaftor, phenobarbital, phenytoin, rifabutin, rifampicin, mitotane, St. John's wort ( Hypericum perforatum )

Source: The list is adapted from the Novartis Institutes for Biomedical PK Sciences internal memorandum (Jan 2018): drug-drug interactions (DDI) database, which is compiled primarily from the Indiana University School of Medicine's "Clinically Relevant" Table (medicine.iupui.edu/flockhart/table.htm), the University of Washington's Drug Interaction Database (druginteractioninfo.org), and the FDA's "Guidance for Industry, Drug Interaction Studies" This may not be an exhaustive list, will be updated periodically.

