**Table 6-7 Drugs with a known risk of Torsades des Pointes prohibited while on study**

Class of medication	Drug Name
With Known risk of Torsades des Pointes	amiodarone, anagrelide, arsenic trioxide, astemizole, azithromycin, chloroquine, chlorpromazine, cilostazol, ciprofloxacin, cisapride, citalopram, clarithromycin, disopyramide, dofetilide, domperidone, donepezil, dronedarone,

Class of medication	Drug Name
	droperidol, erythromycin, escitalopram, flecainide, fluconazole, gatifloxacin, halofantrine, haloperidol, ibutilide, levofloxacin, levomepromazine, levosulpiride, methadone, moxifloxacin, ondansetron, oxaliplatin, papaverine HCl (intra-coronary), pentamidine, pimozide, procainamide, propofol, quinidine, roxithromycin, sevoflurane, sotalol, sulpiride, sultopride, terlipressin, terodilene, thioridazine, vandetanib
This may not be an exhaustive list. Check: crediblemeds.org/healthcare-providers/drug-list for the most updated list.	

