### 7.1.4 Discontinuation of study treatment

Patients may voluntarily discontinue from the study treatment for any reason at any time. If a patient decides to discontinue from the study treatment, the investigator should make a reasonable effort (e.g. telephone, e-mail, letter) to understand the primary reason for this decision and record this information in the patient's chart and on the appropriate CRF pages. They may be considered withdrawn if they state an intention to withdraw, fail to return for visits, or become lost to follow-up for any other reason.

The investigator should discontinue study treatment for a given patient if, on balance, he/she believes that continuation would be detrimental to the patient's well-being.

Study treatment must be discontinued under the following circumstances:

- Emergence of specific adverse events or laboratory abnormalities under some circumstances as outlined in [Section 6](#)
- Pregnancy (pregnancy will be followed for outcome)
- Use of prohibited treatments (refer to [Section 6.4.3](#))
- Any protocol deviation that results in a significant risk to the patient's safety

Patients who discontinue INC280 treatment should NOT be considered withdrawn from the study. They should return for the assessments indicated in [Section 7.2.1](#). If they fail to return for these assessments for unknown reasons, every effort (e.g. telephone, email, letter) should be made to contact them as specified in [Section 7.1.7](#).

The investigator must also contact the IRT to register the patient's discontinuation from study treatment.

Patients who become pregnant must cease all tumor assessments regardless of whether or not they developed Progressive Disease according to BIRC.

Patients who discontinue INC280 should be scheduled for an EOT visit as soon as possible and within 7 days of the last dose of INC280, at which time all of the assessments listed for the EOT visit will be performed. If a patient is discontinued from treatment at a study visit, the assessments performed at that visit will be considered as EOT assessments and do not need to be repeated. An End of Treatment Phase Disposition eCRF page should be completed, giving the date and reason for stopping treatment.

Patients who discontinue study treatment should enter either the survival follow-up period or continue tumor assessments, when appropriate.

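### The complicated-diarrhea example in Table 6-4 names fluoroquinolones, four of which Table 6-7 prohibits for Torsades risk, and Table 6-4 never refers to Table 6-7

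*Protocol*

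**What the plan says.** The diarrhea row of Protocol Table 6-4 leaves treatment to local practice and the investigator's judgment, allows a published guideline to be followed, and then gives examples. For complicated diarrhea (all grade 3 or 4, and grade 1 or 2 with complicating signs such as fever, neutropenia or dehydration), the example includes intravenous fluids, consideration of octreotide, and "antibiotics (e.g. fluoroquinolone) should be given".

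Section 6.4.3 prohibits drugs with a known risk of Torsades des Pointes and refers to Table 6-7. That table includes "chlorpromazine, cilostazol, ciprofloxacin, cisapride, citalopram" and, further on, "gatifloxacin, halofantrine, haloperidol, ibutilide, levofloxacin, levomepromazine, levosulpiride, methadone, moxifloxacin". It warns that it may not be exhaustive.

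Section 7.1.4 lists the circumstances in which study treatment must be discontinued. One of them begins "Use of prohibited treatments (refer to" and points to Section 6.4.3. Section 6.4 sets the general rule that concomitant medication is allowed "except when specifically prohibited (see" Section 6.4.3).

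The cardiac row of Table 6-4 asks for a review of concomitant drugs when QTcF is 501 ms or more. For drugs with the potential "and/or to prolong the QT-interval" it cites Table 6-6, whose only entries are strong CYP3A4 inducers: "carbamazepine, enzalutamide, lumacaftor, phenobarbital, phenytoin, rifabutin, rifampicin" and two others.

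**The concern.** Table 6-4 is what a site will open when a patient has a toxicity. For complicated diarrhea it names one antibiotic class, and four members of that class are on the trial's own prohibited list. Neither the row nor the rest of the table refers to that list.

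Two things are at stake. The first is safety: a drug barred for arrhythmia risk could be given to a patient who may be dehydrated. The second is avoidable loss of treatment: using a listed drug triggers mandatory discontinuation under Section 7.1.4, where the diarrhea alone would have led to a hold and a dose reduction.

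The wrong table number in the cardiac row is a separate slip. A clinician dealing with a prolonged QTcF is sent to a table of enzyme inducers instead of the Torsades list.

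**Working it through.** There is no sample size, power or error rate to reproduce. The check sets the texts side by side, counts, and then bounds the number of patients.

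**Step 1. The texts side by side**

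| Place in Protocol | What it does |
|---|---|
| Table 6-4, diarrhea row | Gives antibiotics as example care for complicated diarrhea; the only class named is fluoroquinolone |
| Section 6.4.1 | Permits oral or topical antibiotics, with no exception on that line |
| Section 6.4.3 and Table 6-7 | Prohibit drugs with known Torsades risk |
| Section 7.1.4 | Requires INC280 to be discontinued on use of a prohibited treatment |
| Table 6-3, diarrhea, row beginning "Grade 3 or 4 (despite maximal anti-diarrheal medication" | Holds INC280 until grade 1 or lower, then resumes one dose level lower |

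A site that follows the first row with a listed drug falls under the fourth row instead of the fifth.

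**Step 2. Fluoroquinolones in Table 6-7**

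Ciprofloxacin, gatifloxacin, levofloxacin and moxifloxacin: 4.

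**Step 3. Cross-references inside Table 6-4**

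- The cardiac row cites Table 6-5 (CYP3A4/5 inhibition) and Table 6-6 (QT prolongation).
- The footnote cites Table 6-3 for dose modifications.
- References to Table 6-7 or Section 6.4.3: 0.

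The Table 6-5 reference is right, since that table lists the strong CYP3A inhibitors. The Table 6-6 reference is wrong, because the Torsades list is Table 6-7.

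**Step 4. How many patients**

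The documents do not say how many patients had complicated diarrhea or were given antibiotics for it. Section 1.2.1.2.1 gives related events in this study, and the Amendment 6 rationale gives 302 patients in the safety assessment.

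- Related diarrhea of any grade: 35/302 = 11.6%, which reproduces the printed figure and confirms the denominator.
- Lowest entry in the related grade 3/4 list: 5/302 = 1.7%. Diarrhea is not in that list.
- *Assumption:* the list is complete down to 5 patients. Related grade 3/4 diarrhea then occurred in at most 4 patients, a range of 0/302 = 0% to 4/302 = 1.3%.

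The list is introduced as what the events included, so it may not be complete. The range also leaves out complicated grade 1 or 2 cases and diarrhea not attributed to INC280, both of which Table 6-4 covers.

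**The case against.** The strongest reply is that the two texts can be obeyed together. The fluoroquinolone is an illustration within optional guidance, and a site can give an antibiotic that is not prohibited. Section 6.4 makes the prohibition prevail. Section 6.3.5, shortly after Table 6-4, says that supportive care for diarrhea is covered in both Section 6.3 and Section 6.4, so a reader is directed to Section 6.4 generally. The Table 6-4 footnote also describes the table as a monitoring schedule only. All of this stands, and it is why the point is minor. It settles which text wins, but it does not remove the unsuitable example or warn someone reading the row during an acute event.

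The second reply is that the arrhythmia risk is small. Section 1.2.1.2.4 reports no QT signal for INC280: among 110 patients, no new QTcF above 500 ms and no increase above 60 ms. Table 6-3 holds INC280 for persistent grade 2 and for grade 3 or 4 diarrhea, and the half-life is 3.5 to 6.3 hours, so combined exposure would often be short. This lowers the risk. But the prohibition applies while on study, the antibiotic's own risk remains, and Section 8.1.3.1 keeps QTc prolongation as an event of special interest.

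The third reply is that the 0% to 1.3% range is weak. That is fair. It is illustrative only, rests on an unverified reading of the list, and covers only part of the group to which the example applies.

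**Conclusion.** The concern holds, at minor severity. The diarrhea example is not aligned with the protocol's own prohibited list: four fluoroquinolones are affected and Table 6-4 has no reference to Table 6-7. The QT cross-reference in the cardiac row is wrong outright. No site is compelled to use a listed drug, and tumor follow-up continues after INC280 is stopped, so what remains is a safety risk and avoidable loss of treatment in a few patients at most.

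The textual findings rest on no assumption. The size does: the only bound available, 0 to 4 of 302 patients with related grade 3/4 diarrhea, depends on the published list being complete to its lowest entry. How many would receive a listed antibiotic is unknown.

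**What to change.** Make two changes in Table 6-4:

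1. In the diarrhea row, replace the fluoroquinolone example with wording such as: antibiotics, excluding agents with known TdP risk (Table 6-7). Naming a permitted antibiotic would also do.
2. In the cardiac row, change the reference for QT-prolonging drugs from Table 6-6 to Table 6-7.

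Both can go out by amendment or by letter to sites. The cost is two wording corrections in one table, with no change to any endpoint, analysis or sample size.

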### **1.2.1.2 Clinical experience**

#### **1.2.1.2.1 Clinical safety and tolerability**

As of the cut-off date of 28-Sep-2018, a total of 1253 cancer patients and 236 non-cancer subjects have received INC280. A total of 709 patients with solid tumors have been treated with INC280 as a single agent, and 544 patients have been treated with INC280 in combination therapies. Fourteen [REDACTED]

[REDACTED] 6 patients in single agent studies and 13 in combination studies. For more information, please refer to the current INC280 [Investigator's Brochure].

Overall INC280 has been well tolerated by patients and the majority of the adverse events (AEs) reported with INC280 single agent have been of mild or moderate severity. The most [REDACTED]

frequent AEs suspected to be related to INC280 of any grade reported in the [CINC280A2201] study, which remains as the reference study for the safety profile of INC280 monotherapy, were edema peripheral (122 patients, [40.4%]), nausea (99 patients, [32.8%]), blood creatinine increased (58 patients, [19.2%]), vomiting (58 patients, [19.2%]), decreased appetite (40 patients, [13.2] and fatigue (40 patients, [13.2%]) and diarrhea (35 patients, [11.6]) and the majority were Grade 1/2. The Grade 3/4 AEs suspected to be related to INC280 in the [CINC280A2201] study included edema peripheral (19 patients, [6.3]) and lipase increased (15 patients, [5.0%]), fatigue (10 patients, [3.3%]), alanine aminotransferase increased (12 patients, [4.0%]), vomiting (6 patients, [2.0%]), nausea and hypophosphatemia (each in 5 patients, [1.7%]), aspartate aminotransferase (5 patients, [1.7%]).

The safety profile of INC280 (capmatinib) has been confirmed to be manageable across all cohorts in INC280A2201 and no new safety signals have been observed.

Pneumonitis and ILD have been reported from both INC280 single agent and combination studies with the EGFR TKIs, including events with fatal outcome. Investigators are advised to carefully monitor patients for signs and symptoms of pneumonitis and implement dose modification and follow up evaluations described in the protocol in all INC280 studies, both single agent and in combination studies.

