Grade 2	
Mandatory: Interrupt INC280 dose during diagnostic workup for ILD until improvement to <math>\leq</math> Grade 1. Exclude infections and other etiologies.
 
In presence of diagnosis of ILD/Pneumonitis after diagnostic workup, it is mandatory to permanently discontinue INC280.
 
Only in absence of diagnosis of ILD/Pneumonitis, study drug may be restarted following these guidelines:
 
 
• If resolves to <math>\leq</math> Grade 1 in <math>\leq</math> 7 days reduce study drug by 1 dose level
 
• If fails to resolve to <math>\leq</math> Grade 1 within 7 days or recurs after resumption of study drug at decreased dose, permanently discontinue INC280
 

Grade 3 and Grade 4	Mandatory: Permanently discontinue study drug

Recommended dose modifications for INC280	
Worst toxicity CTCAE Grade a	During a cycle of therapy
	Treat with IV steroids as clinically indicated. Oxygen therapy as indicated.
Fatigue/ Asthenia (General disorders and administration site conditions)	
Grade 1 or 2	Maintain dose level
Grade 3	Omit dose until resolved to ≤ grade 1, then: If resolved in ≤ 7 days, resume treatment at same dose level If resolved in > 7 days, resume treatment at ↓ 1 dose level
Peripheral edema	
Grade 1 or 2	Maintain dose level
Grade 3	Discontinue dose until resolved to ≤ Grade 1, then ↓ 1 dose level
Other adverse events	
Grade 1 or 2	Maintain dose level, consider to initiate appropriate support medication. For any intolerable grade 2 (e.g.: limiting instrumental ADL), consider omitting the dose until resolved to ≤ grade 1, then ↓ 1 dose level.
Grade 3	Omit dose until resolved to ≤ grade 2, then ↓ 1 dose level
Grade 4	Omit dose and then discontinue from study drug treatment
All dose modifications should be based on the worst preceding toxicity. a Common Toxicity Criteria for Adverse Events (CTCAE Version 4.03).	
b "Combined" defined as: total bilirubin increase to the defined threshold concurrently with ALT/AST increase to the defined threshold	
c "Cholestasis" defined as: ALP elevation (> 2.0 x ULN and R value (ALT/ALP in x ULN) < 2.0) in patients without bone metastasis, or elevation of ALP liver fraction in patients with bone metastasis	

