### 6.3.4 Follow-up for toxicities

All patients will be followed for safety until 30 days after the last dose of INC280. Patients whose treatment is temporarily interrupted or permanently discontinued due to an AE or abnormal laboratory value must be followed until resolution or stabilization of the event, whichever comes first, including all study assessments appropriate to monitor the event.

An unscheduled assessment should be performed in all cases below where toxicity monitoring is recommended more frequently than defined by the schedule of assessments. Subsequent monitoring must be performed as per the regular visit schedule.

All patients should receive best supportive care (BSC) as per standard local practice for the treatment of pre-existing medical conditions or adverse events that may arise during the study. BSC is defined as drug or non-drug therapies, nutritional support, physical therapy, or any other treatment alternative that the investigator believes to be in the patient's best interest, but excluding other anti-neoplastic treatments (with the exception of radiotherapy for control of bone metastases – see [Section 6.4.1](#)).

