SKIN TOXICITY (rash and photosensitivity)  CTCAE grade 1  CTCAE grade 2  ≥ CTCAE grade 3	
Consider to initiate institute appropriate skin toxicity therapy (such as antihistamines, topical corticosteroids and low-dose systemic corticosteroids)
 
Initiate/intensify appropriate skin toxicity therapy (such as antihistamines, topical corticosteroids and low-dose systemic corticosteroids).
 
Intensify appropriate skin toxicity therapy and monitor weekly or more frequently until resolved to grade ≤ 2

TOXICITY	FOLLOW-UP EVALUATION
Peripheral edema ≤ CTCAE grade 2	Consider to initiate conservative measures such as leg elevation, compression stockings, and dietary salt modification as clinically indicated
≥ CTCAE grade 3	Initiate/intensify conservative measures
RESPIRATORY DISORDERS ILD /Pneumonitis	
CTCAE Grade 1	CT scan (high-resolution with lung windows) recommended, with serial imaging to monitor for resolution or progression - re-image at least every 3 weeks Monitor for symptoms every 2-3 days - Clinical evaluation and laboratory work-up for infection Monitoring of oxygenation via pulse oximetry recommended Consultation of pulmonologist recommended
CTCAE Grade 2	CT scan (high-resolution with lung windows) 
 
Monitor symptoms daily, consider hospitalization
 
Clinical evaluation and laboratory work up for infection
 
Consult pulmonologist
 
Pulmonary function tests a - if normal at baseline, repeat every 8 weeks
 
Bronchoscopy with biopsy and/or BAL recommended c
 
Symptomatic therapy including corticosteroids if clinically indicated (1 to 2 mg/kg/day prednisone or equivalent as clinically indicated) b
 

CTCAE Grade 3 and Grade 4	CT scan (high-resolution with lung windows) Clinical evaluation and laboratory work-up for infection Consult pulmonologist Pulmonary function tests a - if < normal, repeat every 8 weeks until ≥ normal Bronchoscopy with biopsy and/or BAL if possible c Treat with IV steroids (methylprednisolone 125 mg) as indicated. When symptoms improve to ≤ Grade 1, a high dose oral steroid (prednisone 1 to 2 mg/kg once per day or dexamethasone 4 mg every 4 hours) b . If IV steroids followed by high dose oral steroids does not reduce initial symptoms within 48 to 72 hours, consider non-corticosteroid immunosuppressive medication

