\*Note: this table refers only to the evaluation schedule to monitor selected toxicities. Refer to [Table 6-3](#) for dose modifications required for applicable toxicities

\*\*Note: except if the patient is Grade 2 at baseline in which case: it is ≥ CTCAE grade 3

a PFT (Pulmonary function tests) to include: diffusing capacity corrected for hemoglobin (DLCO); spirometry; resting oxygen saturation

Guideline for significant deterioration in lung function: Decrease in spirometry and/or DLCO of 30% and/or O2 saturation ≤ 88% at rest on room air.

b Duration and dose of course of corticosteroids will vary according to circumstances but should be as limited as possible. Consider tapering dosage at end.

c If bronchoscopy is performed, bronchoalveolar lavage (BAL) should be done where possible to exclude alveolar hemorrhage, opportunistic infections, cell count + determination lymphocyte CD4/8 count where possible.

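### Table 6-4, grade 3/4 ILD/pneumonitis: the written trigger for the step after steroids conflicts with the condition for starting oral steroids, and the start of its 48 to 72 hour period is not stated

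*Protocol*

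**What the plan says.** The ILD/pneumonitis row of Protocol Table 6-4, for CTCAE grades 3 and 4, contains three treatment statements in sequence:

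1. "Treat with IV steroids (methylprednisolone 125 mg) as indicated".
2. "When symptoms improve to ≤ Grade 1, a high dose oral steroid", followed by examples of the oral agent. Footnote b is attached here.
3. "If IV steroids followed by high dose oral steroids does not reduce initial symptoms within 48 to 72 hours, consider non-corticosteroid immunosuppressive medication".

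The same cell also asks, without condition, for a pulmonologist to be consulted.

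Footnote b says of the steroid course: "Duration and dose of course of corticosteroids will vary according to circumstances but should be as limited as possible". The corresponding row of Table 6-3 makes permanent discontinuation of INC280 mandatory at grades 3 and 4 and adds: "Treat with IV steroids as clinically indicated. Oxygen therapy as indicated". Section 6.3.4, which introduces Table 6-4, states the general rule: "All patients should receive best supportive care (BSC) as per standard local practice".

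**The concern.** The third statement is the only written step beyond steroids for the most severe grades of this toxicity. It is evidently meant for patients whose symptoms do not respond. Yet it is conditional on an oral course that the preceding statement ties to a good response.

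The topic is not a minor one. Section 8.1.3.1 lists ILD/pneumonitis among the adverse events of special interest, and Section 1.2.1.2.1 reports: "Pneumonitis and ILD have been reported from both INC280 single agent and combination studies with the EGFR TKIs, including events with fatal outcome". The same section advises investigators to carry out the follow-up evaluations that the protocol describes. Sites told to follow a sequence should be able to tell when each step applies. Here they have to interpret it, and they may interpret it differently.

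**Working it through.** No figure is involved, so this is a check of logic on the text.

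**Inputs, all from the grade 3/4 row of Table 6-4**

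- G: symptoms have improved from grade 3/4 to grade 1 or less.
- O: the high dose oral steroid has been started. The row describes this for G and gives no other entry point.
- N: the initial symptoms have not been reduced within 48 to 72 hours.
- S: the trigger for considering non-corticosteroid immunosuppressive medication is met.

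**Relations as written**

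- O is described when G holds.
- S needs O (IV steroids followed by oral steroids) and N.
- G is itself a reduction of the initial symptoms, so a patient for whom G holds does not satisfy N.

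**Cases**

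- *No improvement on IV steroids.* G fails, so the described point for O is not reached. IV followed by oral has not occurred, and S is not met.
- *Improvement to grade 2.* G still fails and O is still not reached. S is not met.
- *Improvement to grade 1 or less.* G holds and O starts. The initial symptoms have been reduced, so N fails and S is not met.
- *Improvement, oral steroids, then relapse.* This is a different situation, which the row does not address. Even if S were read to cover it, that would give no trigger for a patient who never improved.

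**The time window.** The period of 48 to 72 hours could be counted from the onset of the event, from the first IV dose or from the change to oral steroids. The row does not say which. The last of these is not available for a patient who has not improved.

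**Whether another passage supplies the trigger**

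- Footnote b allows the dose and duration of corticosteroids to vary. It does not address when oral steroids begin.
- The grade 3/4 row of Table 6-3 mentions IV steroids and oxygen and no later step.
- The grade 2 row of Table 6-4 has its own corticosteroid line, which is not linked to the grade 3/4 sequence.

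None of these resolves the conflict.

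**The case against.** The strongest reply is that the row is supportive-care guidance and not an algorithm. Its verbs are permissive (as indicated, consider), and the oral steroid statement is shorthand without a main verb. The text says when symptoms improve, not only when they improve, so treating the condition as exclusive is an inference. A note under Table 6-4 describes the table as an evaluation schedule and sends the reader to Table 6-3 for dose modification, where the grade 3/4 rule for study drug is clear.

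Much of this stands. A reader might infer that non-responding patients are excluded from escalation, or that a site must depart from the protocol to treat them. The documents do not support either reading. Section 6.3.4 provides for best supportive care by local practice, including other treatment that the investigator judges to be in the patient's interest. Section 6.4 permits concomitant medication needed for the patient's care unless it is specifically prohibited, and Section 6.4.3 with Tables 6-6 and 6-7 does not prohibit immunosuppressants as a class. A suggestion to consider a treatment in one circumstance does not forbid it in others.

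Nor do the documents support a claim about frequency. They give no number of grade 3/4 ILD cases that failed IV steroids, and they do not link the reported fatal events to this wording. The Amendment 6 rationale shows several cohorts already closed or fully enrolled, and exclusion criterion 22 keeps out patients with present or past ILD.

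What the reply does not do is make the two statements consistent. No second route to oral steroids and no second trigger is written, and the start of the time window is missing on any reading.

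**Conclusion.** The inconsistency is real and confined to one table cell. Read as written, a grade 3/4 patient who does not improve on IV steroids does not meet the stated trigger for the next step, and the start of the 48 to 72 hour period is undefined. This rests on two readings: that improvement to grade 1 or less is the described entry point for oral steroids, and that such an improvement counts as a reduction of the initial symptoms.

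The defect is an inconsistent written trigger, not exclusion from care. Study drug is already permanently discontinued at these grades, so its dosing does not change. The primary analysis, alpha and power are untouched. The case for correcting it rests on the seriousness of the event and on clarity for sites, not on a count of affected patients.

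**What to change.** Reconcile the two statements in the grade 3/4 ILD/pneumonitis row of Table 6-4 so that the condition for oral steroids and the condition for the following step can both be met. State from when the 48 to 72 hours run for a patient who has not improved on IV steroids. Which trigger and which starting point apply is for the sponsor's medical team to decide; no clinical rule is proposed here.

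The cost is the rewording of one table cell at the next amendment. It adds no procedure and no data collection, and it changes nothing in the SAP.
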